#### 6.6.1.2 Discontinuation of Study Drug

Participants may be prematurely discontinued from study drug prior to completing a full 7 consecutive days of study drug (i.e., 14 doses administered BID) for any of the following reasons:

- Withdrawal from study or Lost to follow-up (due to reasons listed in Section 6.6.1.1)
- Participant decision (i.e., to be used as reason if participant desires to stop study drug but not withdrawal consent of the study). A participant is free to discontinue study drug therapy at any time without prejudice to further treatment. The Investigator must verify on the eCRF that the participant decision was not based on an adverse event (AE). In such cases, the reason must be recorded as premature discontinuation from study drug due to an AE.
- AE (e.g., continuation of study drug poses a risk to the participant as judged by the Investigator)
- Positive pregnancy test at any time during study drug treatment, OR
- Early discontinuation/termination of the study by Sponsor

In the event that a participant prematurely discontinues study drug, all study procedures and assessments should continue to be performed and collected until the participant completes the EOS/Day 60 visit to the extent possible.

#### 6.6.1.3 Replacement of Participants

Randomized participants may not be replaced.

# 6.6.2 Discontinuation or Termination of the Study

An independent Data Monitoring Committee (DMC) will be formed and constituted according to appropriate regulatory agency guidelines. Detailed information regarding the composition of the committee and detailed procedures will be provided in a separate DMC charter. The independent DMC will review the safety, tolerability, and efficacy data of Study Part 1 and Study Part 2 as described in the DMC charter.

An emergency DMC meeting will convene if 3 or more blinded participants in Study Part 1 or 10 or more blinded participants in Study Part 2 experience AEs leading to premature discontinuation of study drug.

The Sponsor may discontinue further enrollment of the study at any time (including after unblinding of Study Part 1 study data and before enrollment of Study Part 2).

Additionally, the Sponsor may (before beginning enrollment of Study Part 2):

- Exclude a specific patient subgroup due to potential safety concerns
- Modify allowed concomitant medication due to potential safety concerns, OR
- Modify other protocol criteria due to potential safety concerns (e.g., safety laboratory monitoring or PK sampling)
- Modify the sample size and/or endpoints of Study Part 2 if Study Part 1 efficacy data suggests that such changes may be necessary to adequately power Study Part 2

The DMC may also recommend interruption of recruitment at ANY time during Study Part 1 or Study Part 2 for further analysis. The DMC may also recommend termination of the study if any one of the following are observed and not associated with the natural course of COVID-19 (based on CTCAE v5:

https://ctep.cancer.gov/protocoldevelopment/electronic\_applications/docs/CTCAE\_v5\_Quick Reference 5x7.pdf):

- Grade 4 or greater nausea, vomiting, diarrhea, or abdominal pain lasting >72 hours in participants who have received maximal medical care
- Grade 4 or greater anemia, neutropenia, or thrombocytopenia without an alternative etiology

The DMC will review the study on a regular basis as outlined in the DMC charter and evaluate the study for safety, futility or lack of efficacy. The DMC may recommend interruption of recruitment or termination of the study at any time. Any recommendations for safety review, as summarized in section 6.4. are non-binding. The DMC is fully independent and is at liberty to use additional or modified criteria as a basis for determination of the safety, tolerability and potential futility in Study Part 1 or Study Part 2.

#### 7 STUDY INTERVENTIONS

## 7.1 Description of Products

The investigational product is a capsule containing 250 mg of active pharmaceutical ingredient (API) or matching placebo.

#### 7.1.1 Active Intervention – ANA001

#### 7.1.1.1 Formulation, Storage, Preparation, and Handling

For Study Part 1 and Study Part 2 ANA001 (proprietary niclosamide formulation) 250 mg capsules will be provided in bottles containing a sufficient number of capsules (56 per patient) to cover the 7-day treatment period and should be stored at room temperature out of direct sunlight.

#### 7.1.1.2 Dosing and Administration

ANA001 will be administered as 1,000 mg (4 capsules; 250 mg each) PO BID for 7 consecutive days and should be given with a meal. If the participant requires mechanical ventilation over the course of the study, niclosamide may be administered via NG, OG, or PEG tube and, if possible, should be administered with a scheduled NG, OG, or PEG feeding. Please refer to the study Pharmacy Manual for additional dosing and study drug administration information.

#### 7.1.2 Control - Placebo

#### 7.1.2.1 Formulation, Storage, Preparation, and Handling

For Study Part 1 and Study Part 2, matching placebo (size 0, hydroxypropylmethylcellulose [HPMC]) will be provided in bottles containing a sufficient number of capsules (56 per patient) to provide for dosing for the 7-day treatment duration. Placebo should be stored at room temperature out of direct sunlight.

Placebo formulation is comprised of generally recognized as safe (GRAS) excipients and contains fillers (microcrystalline cellulose and mannitol), a binder (hydroxypropyl cellulose), a disintegrant (sodium starch glycolate), a wetting agent (sodium lauryl sulfate), a glidant (colloidal silica), and a lubricant (sodium stearyl fumarate). No biologically active or potentially immunogenic compounds are included in the placebo formulation.

## 7.1.2.2 Dosing and Administration

Placebo will be administered as 4 HPMC capsules PO BID for 7 consecutive days and should be given with a meal. If the participant requires mechanical ventilation over the course of the study, placebo may be administered via NG, OG, or PEG tube and, if possible, should be administered with a scheduled NG, OG, or PEG feeding. Please refer to the study Pharmacy Manual for additional dosing and study drug administration information.

#### 7.2 Dosing Assignment and Bias Minimization

Both Study Part 1 and Study Part 2 are randomized and double-blinded to reduce bias.

#### 7.2.1 Dosing Allocation

During Study Parts 1 and 2, participants will receive either ANA001 as a 1,000 mg PO BID dose or matching placebo dose for 7 days.

#### 7.2.2 Randomization Strategy and Procedure

During Study Part 1 and Study Part 2 participants will be randomized in a 1:1 ratio to ANA001 or matching placebo.

The randomization plan will be overseen by the study statistician. The randomization code and resulting allocation list will be generated and overseen by the study statistician. The list will be blocked and stratified by oxygenation (SpO2 <93 and <98% on room air versus SpO2  $\leq$ 93% on room air), diarrhea (presence/absence), and age ( $\leq$ 65/ $\leq$ 65).

#### 7.2.3 Extent and Maintenance of Blinding

Both Study Part 1 and Study Part 2 will be blinded. The containers of study drug product allocated to each participant will not identify treatment allocation. Treating Investigators will be blinded. The DMC statistician and the DMC itself will be unblinded for analysis purposes as described in the DMC charter. The Sponsor may also be unblinded at any time if the Sponsor deems this necessary to adequately evaluate potential safety issues. The Sponsor may also be unblinded in accordance with procedures outlined in the statistical analysis plan (SAP).

#### 7.2.4 Unblinding Procedures

#### 7.2.4.1 Planned Unblinding

The Sponsor and/or principal investigator may decide to unblind the study drug for a given participant if medically necessary. The investigator may request being unblinded to treatment assignment of a participant, in accordance with procedures outlined in the Randomization and Trial Supply Management (RTSM) Manual

#### 7.2.4.2 Unplanned or Unintentional Unblinding

The Sponsor or designated representative must be notified immediately if an Investigator and/or blinded site study team member becomes unblinded unintentionally.

#### 7.3 Assessment and Verification of Compliance

ANA001 or matching placebo will be administered to the participants by clinical staff. For participants who are discharged prior to completing the 7-day course of treatment, the remainder of the 7-day course of study drug will be provided for at-home administration in a bottle along with a diary card on which they are to record the dates/times/amount of study drug self-administered. Participants are to return the bottle and the diary card at the time of their follow-up visit to the Investigator. In the event that telemedicine follow-up is necessary arrangements to obtain the bottle and the diary card must be made as outlined in the Randomization and Trial Supply Management (RTSM) Manual.

Participants should be advised not to consume alcohol or alcohol containing products while on study drug due to the potential for ANA001 to potential increased impairment (Yomesan [PI] 2008: https://www.bayer.co.za/static/documents/MSDS/PIs/YOMESAN\_EN\_PI.pdf).

#### 7.4 Prior and Concomitant Therapies

All prescription and over-the-counter systemic (i.e. oral, intravenous, intramuscular, inhaled, subcutaneous, or systemically absorbed transdermal) medications being administered or being taken by the participant from prior to randomization (considered prior medications) and from randomization through the Day 60 visit (considered concomitant medications). For the purpose of this study, all enteral nutrition and administration of blood products will also be considered as medication.

The medication, dose, route of administration, duration (e.g., start date and time and stop date and time), and reason for the medication (including if the medication was given as a primary or supportive therapy for COVID-19) must be documented on the appropriate eCRF(s).

At each assessment timepoint post-hospitalization, the participant will be asked about any medications taken and these will be recorded in the participant's record and documented on the appropriate eCRF(s).

Any medication, which is considered necessary for the patient's safety and wellbeing, may be given at the discretion of the Investigator and must be recorded in the appropriate sections of the participant's record and documented on the appropriate eCRF(s).

The Sponsor recognizes that new therapies for COVID-19 may become available during the time this study is being conducted. Therapeutics approved by the FDA and listed in CDC guidelines, or FDA authorized medications (i.e., under the emergency-use authorization program) to prevent or treat COVID-19 and offered by the respective study site as standard-of-care may be administered and must be meticulously documented as outlined above.

#### 7.4.1 Prohibited Therapies

Patients receiving chemotherapeutic agents and/or immunomodulators (e.g., systemic glucocorticoids, Mabs or plasma transfusions) for chronic disease conditions (e.g., malignancies, rheumatoid arthritis or other autoimmune diseases) at screening will not be eligible for enrollment into this study. Such agents may be administered as standard-of-care after enrollment and should be captured on the appropriate eCRF(s) as outlined above.

Participants should be advised not to consume alcohol or alcohol containing products while on study drug due to the potential for ANA001 to potential increased impairment (Yomesan [PI] 2008: https://www.bayer.co.za/static/documents/MSDS/PIs/YOMESAN EN PI.pdf).

#### 7.4.2 Permitted Therapies

Therapeutics approved by the FDA and listed in CDC guidelines, or FDA authorized medications (i.e., under emergency-use authorization program) to prevent or treat COVID-19 and offered by the respective study site as standard-of-care may be administered and must be meticulously documented as outlined above.

Specifically, patients who deteriorate such that they fulfill criteria for more severe COVID-19 (e.g., require mechanical ventilation or increased oxygen support) may receive all treatments and FDA approved or FDA authorized medications determined by the respective investigative site to constitute standard-of-care for the treatment of severe or critical COVID-19 and should remain in the study.

## 7.4.3 Rescue Therapies

Rescue therapy is defined as any therapy that is either FDA approved (or has FDA emergency-use authorization) for COVID-19 or is administered to a participant to treat COVID-19 based on the potential for clinical efficacy against SARS-CoV-2. As the available FDA approved or authorized therapies are likely to evolve during enrollment of this study, a complete list of such therapies identified in the course of this study will be generated prior to unblinding.

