T /	Part 2 (approximately 376 participants): 188 ANA001 + 188 matching placebo
Intervention	ANA001 1,000 mg PO BID or matching placebo for 7 days (i.e., 14 scheduled doses comprised of 56 capsules in total): All participants will also receive unrestricted access to standard-of-care as defined by the respective study sites.
Primary Objective and	Objective:
Primary Endpoints/Parameters	To evaluate the safety and tolerability of ANA001 as therapy for moderate
(Part 1)	and severe COVID-19 patients Endpoints/Parameters:
(- ··- v *)	Treatment-emergent adverse events (TEAEs), treatment-emergent serious
	adverse events (SAEs), deaths, and discontinuations due to a TEAE
	Vital signs and laboratory (hematology, chemistry, and coagulation) parameters
Secondary Objectives and Secondary Endpoints (Part 1)	Objectives:  • To evaluate the efficacy of ANA001 as therapy in moderate and severe COVID-19 patients

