To evaluate the effect of ANA001 on requirement for oxygen and/or assisted ventilation	
 
Proportion of participants requiring supplemental O2, high-flow nasal cannula (HFNC) oxygen, noninvasive positive pressure ventilation (NIPPV) or mechanical ventilation on Day 8 and Day 15
 
Mean number of days on mechanical ventilation within 15 days after enrollment
 
Mean number of oxygenation-free days within 15 days after enrollment
 

To evaluate time to resolution of the WHO Ordinal Scale for Clinical Improvement	
 
Proportion of participants who achieve a score of 1 in the WHO Ordinal Scale for Clinical Improvement (Appendix 1) on Day 8 and Day 15
 
Median time (in hours) to a 2-point improvement in the WHO Ordinal Scale for Clinical Improvement
 
Incidence and severity of thromboembolic events within 15 days after enrollment
 

To evaluate the effect of ANA001 on thromboembolic events	Incidence and severity of thromboembolic events within 15 days after enrollment
To evaluate the relationship of ANA001 and markers of inflammation associated with	Incidence of abnormal markers of inflammation to (CRP, IL-6, TF, MCP-1, and IP-10) on Day 8

acute respiratory distress syndrome (ARDS)	
To evaluate the relationship between ANA001 plasma concentrations and viral dynamics	
 
Mean change in viral load from baseline (BL) on Days 1, 4, 8, 15, and 28
 
Mean time (in days) to viral load undetectable by nasopharyngeal (NP) swab
 

Table 3 Objectives and Endpoints of Study Part 2

Objectives	Endpoints/Parameters
Primary	
To evaluate efficacy of ANA001 as therapy for COVID-19 patients, AND	Time to clinical improvement measured as median time (in hours) to hospital discharge (where discharge is defined as a score of 1 or 2 in the WHO Ordinal Scale for Clinical Improvement)
To evaluate the safety and tolerability of ANA001 as therapy for COVID-19 patients	
 
TEAEs, treatment-emergent SAEs, deaths and discontinuations due to a TEAE
 
Vital signs and laboratory (hematology, chemistry, and coagulation)
 

	parameters
Secondary	
To evaluate clinical improvement using NEWS2	Mean change from baseline (BL) in NEWS2 on Day 15
To evaluate the need and duration of rescue therapy	Mean number of days on rescue treatment (COVID-19 treatments that are FDA approved or have emergency-use authorization) within 15 days after enrollment
Exploratory	

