### 5.4 Exclusion Criteria

If an individual meets any of the following criteria at screening, he or she is ineligible for this study:

1. Hospitalized, but no longer requires ongoing inpatient medical care (i.e. hospital discharge is anticipated in ≤24 hours.

- 2. Per the clinical judgment of the Investigator, the patient is not anticipated to survive >48 hours OR is under palliative care.
- 3. Evidence of critical illness, defined by at least 1 of the following:
  - Respiratory failure requiring at least 1 of the following:
    - a. Endotracheal intubation and mechanical ventilation, oxygen delivered by high flow nasal cannula (heated, humidified, oxygen delivered via reinforced nasal cannula at flow rates >20 L/min with fraction of delivered oxygen >0.5)
    - b. Noninvasive positive pressure ventilation (NIPVV), OR
    - c. Extracorporeal membrane oxygenation (ECMO) or clinical diagnosis of respiratory failure (i.e., clinical need for 1 of the preceding therapies, but preceding therapies not able to be administered in setting of resource limitation)
  - Shock (defined by systolic blood pressure (BP) <90 mm Hg, or diastolic BP <60 mm Hg or requiring vasopressors), OR
  - Multi-organ dysfunction/failure
- 4. Severe CNS conditions, e.g., acute stroke, severe confusion, or other acute mental status changes that may significantly determine duration of hospitalization and patient outcomes.
- 5. Chronic kidney disease requiring dialysis.
- 6. Anticipated transfer to another site, which is not a study site, within 72 hours.
- 7. Known allergy to the study drug or salicylate containing medications.
- 8. Suspected and/or confirmed pregnancy or breastfeeding.
- 9. Current or planned participation in any other interventional clinical trial under a US IND or EUA.
- 10. Patients receiving chemotherapeutic agents and/or immunomodulators (including glucocorticoids, monoclonal antibodies (Mabs), or plasma transfusions) for chronic disease conditions (e.g., malignancies, rheumatoid arthritis or other autoimmune diseases).

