- AE assessment (AEs are to be recorded from the time of signing of informed consent to the end of the study participation).
- All systemic prior medications within 14 days prior to screening (Section 7.4).
- Serum pregnancy test for females of childbearing potential.

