#### 9.3.5 Analysis of Secondary Efficacy Endpoints

Mean change from baseline in continuous secondary efficacy endpoints will be compared using an analysis of variance model with baseline values and stratification factors as covariates. Difference in least-squares means and associated 95% confidence intervals will be reported. Sample size permitting, P-values will also be reported.

Logistic regression models, with stratification factors as covariates, will be used to compare categorical secondary endpoints. Odds ratio and corresponding 95% confidence intervals will be reported. P-values will also be reported.

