#### 9.7 **Multiplicity Adjustment**

A hierarchical testing scheme is planned to preserve the familywise type I error of the study. If statistical significance of the primary efficacy endpoint is established, secondary efficacy endpoints will be tested in the following order:

- 1. Mean change from baseline (BL) in National Early Warning Score (NEWS2)
- 2. Mean number of days on rescue treatment (COVID-19 treatments that are approved under NDA or EUA) within 15 days after enrollment

The testing scheme will be halted at the first secondary endpoint that fails to establish statistical significance.

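### The gated Part 2 rescue-days endpoint counts COVID-19 therapy already running at randomization, but the planned model does not adjust for it; the cost is precision only, of unknown size

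*Protocol*

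**What the plan says.** **Endpoint.** Protocol Table 3 lists, as a Part 2 secondary endpoint, "Mean number of days on rescue treatment (COVID-19 treatments that are FDA approved or have emergency-use authorization) within 15 days after enrollment". Section 9.7 places it last in the testing hierarchy, after the primary endpoint and NEWS2: "Mean number of days on rescue treatment (COVID-19 treatments that are approved under NDA or EUA) within 15 days after enrollment".

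**Definition.** Section 7.4.3 begins "Rescue therapy is defined as any therapy that is either FDA approved (or has FDA emergency-use authorization) for COVID-19" and adds therapy given for COVID-19 because it may work against the virus. None of these places requires that the drug be started after randomization or in response to worsening.

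**Same drugs as background care.** The synopsis states: "All participants will also receive unrestricted access to standard-of-care as defined by the respective study sites". Section 7.4.2 says that approved or authorized drugs "offered by the respective study site as standard-of-care may be administered". It mentions deterioration only as a particular case.

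**Entry.** Exclusion 10 in 5.4 bars "immunomodulators (including glucocorticoids, monoclonal antibodies (Mabs), or plasma transfusions) for chronic disease conditions". Treatment for COVID-19 itself is not an exclusion.

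**Model.** For continuous secondary endpoints, 9.3.5 specifies an "analysis of variance model with baseline values and stratification factors as covariates". The stratification factors (7.2.2) are oxygenation, diarrhea and age.

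**SAP.** The SAP covers the end of Part 1 only (SAP 1). For Part 1, SAP 7.5.2 limits rescue to drugs given more than 24 hours after study drug start and within 240 hours of enrollment. Its model uses the stratification factors, baseline WHO score and number of co-existing conditions. It drops participants who needed no rescue treatment.

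**Data.** Section 6.1 collects "All systemic prior medications within 14 days prior to screening". Section 7.4 requires start and stop times and the reason for each drug.

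**The concern.** A hospitalized patient can enter Part 2 in the middle of a COVID-19 course, and its remaining days count as rescue days. Whether a patient is on therapy at entry is then likely to be one of the strongest predictors of the count, and it is known before the first dose. A count of days after enrollment has no baseline value of its own, so the baseline term in 9.3.5 does not capture it. Neither do the stratification factors, except insofar as oxygenation predicts treatment. Copying the SAP 7.5.2 model into Part 2 would not add the term either.

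At stake is the precision of a confirmatory, alpha-controlled endpoint that is reached only if the primary and NEWS2 both succeed. A secondary matter is interpretation. The objective is the need for and duration of rescue, whereas the count measures total use of COVID-19 drugs. Total use is a legitimate quantity, but it is not the same thing.

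**Working it through.** **The plan's own figure.** No SD, effect or power is stated for rescue days. The only figure to reproduce is the primary one: 4(1.960 + 1.036)²/[ln(15/11)]² = 35.9/0.0962 = 373.3, so 374 events, as in 9.1.2. It has no bearing here beyond giving 188 per arm.

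**Formula.** Let p be the share on therapy at entry, d the difference in mean counted days between those on and not on therapy, and s the SD within those groups. A yes/no covariate removes the fraction R² = p(1-p)d²/[s² + p(1-p)d²] of the residual variance. All three inputs are assumptions. Example: p = 0.5, d = 4, s = 4 gives 4/(16 + 4) = 20%, and the standard error falls from 4.47√(2/188) = 0.461 to 4√(2/188) = 0.413 day.

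**Simulation, 188 per arm.** The comparison model contains treatment and the oxygenation stratum; the second model adds therapy at entry. Assumed:
- New rescue in 42% (placebo) v 26.5% (ANA001), starting on Days 2-8, mean 7 days, SD 3.
- Background therapy from Day 1 in 30-90%, mean 5-7 days, SD 2-3.
- Each calendar day counted once, cut at Day 15.
- Uptake equal across oxygenation strata, or 60 points apart.

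At the centre point (50% on therapy, mean 6, SD 2.5, equal uptake), residual SD falls from 4.33 to 3.45. The variance cut is 1 - (3.45/4.33)² = 37%, and power rises from 50% to 69%. The implied d² is (4.33² - 3.45²)/0.25 = 27.4, so d is about 5.2 days. With 20% v 80% uptake by stratum, p(1-p) is 0.16 within each stratum, so R² = 0.16 × 27.4/(11.90 + 4.38) = 27%. This matches the simulated SDs of 4.04 and 3.45. Over the whole grid the cut runs from 9.3% to 46.3%.

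**Routine starts just after randomization.** That grid lets untreated patients start only as new rescue. Sections 6.1 and 6.3 put screening and dosing as soon as possible after hospital presentation, so some patients may start ordinary standard of care on Day 1 or 2. Those days count too, and they shrink d. If half do so, d roughly halves to 2.6. Even with s held at 3.45, R² = 0.25 × 6.84/(11.90 + 1.71) = 13%. Simulated at the centre point (1,500 runs per row):

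| Untreated patients starting on Day 1-2 | Variance cut, equal uptake | Power without / with covariate | Variance cut, 20% v 80% uptake |
|---|---|---|---|
| 0% | 37% | 53% / 71% | 27% |
| 30% | 19% | 46% / 54% | 13% |
| 50% | 11% | 45% / 48% | 7% |
| 70% | 5% | 46% / 46% | 3% |
| 90% | 1% | 48% / 49% | 0.5% |

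(The 27% is from the SDs above. The first-row powers differ from the 50% and 69% above because they come from a separate, shorter run.)

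A separately built simulation with all three stratification factors gave cuts of about 6% to 40%. It gave 7% when oxygenation nearly determined therapy (5% v 95%) and 6% when 80% of untreated patients started later.

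**Type I error.** With no treatment effect, rejection was 4.8-5.0% without the covariate and 4.5-5.4% with it.

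**The case against.** The strongest reply is that the gap may never arise. Section 9 of the protocol gives key details only, and a full SAP for each part is promised. The Part 1 SAP already went beyond 9.3.5 by adding covariates, a timing rule and blinded medication review. Section 9.3.5 is worded for change from baseline, so the model for a day count is still open. If the 24-hour rule in SAP 7.5.2 were carried into Part 2 and *given* meant *started*, running therapy would not count at all. This is fair. But no Part 2 SAP is among the documents, the 24-hour rule is not stated to apply to Part 2, and *given* can also cover later days of a running course. The possibility that a later document settles the matter is no reason not to name the better model now.

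Two further points stand. The simulations did not include baseline WHO score or co-existing conditions. WHO score separates patients on and off oxygen, so it could absorb part of the same variance. And the drug lists differ: 9.7 counts drugs approved or authorized under NDA or EUA, while 7.4.3 is broader. A covariate built on the broader list would flag some patients who have no counted days.

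A reader might infer more than the documents support:
- *That the comparison is biased or its error rate inflated.* It is not. Therapy at entry precedes randomized, blinded treatment.
- *That a substantial gain is assured.* The 9% floor of the first grid (188/(1 - 0.093) = 207 per arm) disappears once routine starts after randomization are allowed.
- *That a new-start count should replace the endpoint.* It is a different estimand. If ANA001 shortens background courses, the all-therapy count can have more power: with a 1-day shortening and the covariate, 89-99% against 79-84% for new starts on the first grid.

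**Conclusion.** The point holds as a low-cost improvement to consider, not as an error in the endpoint. As written, the last gated Part 2 secondary endpoint includes days of therapy already running at randomization, and no stated model adjusts for it. That running courses count is inferred from the absence of a start-time rule; no section says so outright.

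The consequence is limited to avoidable residual variance. The primary endpoint is untouched. Net of the oxygenation stratum, the reduction runs from about 0-1% to about 46%, as if between 188/(1 - 0.005) = 189 and 188/(1 - 0.463) = 350 per arm had been enrolled. Uptake, course length, effect and SD are all assumed, so neither end should be read as an estimate. The gain is negligible if nearly everyone or nobody is on therapy at entry, or if most untreated patients start routine care within a day or two. It is small if oxygenation nearly determines who is treated.

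**What to change.** In the 9.3.5 model for this endpoint, and in the Part 2 SAP, prespecify COVID-19 therapy ongoing at randomization (yes/no) as a covariate. Derive it from the recorded start and stop times. Use the same drug list that defines the counted days, which means first settling whether that is the 9.7 or the 7.4.3 list. Fix the list and the derivation before unblinding. The endpoint and the hierarchy stay as written.

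The cost is one sentence and one degree of freedom; sections 6.1 and 7.4 already require the data.

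If SAP 7.5.2 is reused for Part 2, leave out its exclusion of participants with no rescue treatment and count them as 0 days. A new-start count, with *given* defined as *started* more than 24 hours after first dose, may be reported beside the main count as supportive only. Its limits should be stated: routine care begun after 24 hours still counts, and treatment for worsening within the first 24 hours does not.
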